## **8. RISK/BENEFIT ASSESSMENT**

---

### **8.1 Risks to subjects**

There are four potential risks associated with participation in the proposed study

1. Physical harm associated with assessment procedures
2. Physical harm associated with intervention procedures
3. Emotional distress
4. Loss of confidentiality through email communication

**1. In terms of physical harm associated with assessment procedures,** risks associated with some of the physical tests are minimal. They include minimal risk of falling when completing physical function measures (Timed-Up-and-GO and Short Physical Performance Battery).

**2. In terms of physical harm associated with intervention procedures,** there are few known and possible interactions of EGCG with other drugs. A few possible herb-drug interactions have been reported in a variety of disease settings and animal models. These include possible interactions with adenosine, anticoagulants/antiplatelets, codeine, bortezomib, tamoxifen, verapamil, irinotecan, cytochrome p450 34 substrates, uridine 5'-diphospho-glucuronosyltransferase substrates, acetaminophen, nadolol, and palbociclib. These interactions are possible due to an interaction with EGCG itself or other components within green

tea, e.g. tannin. This product is caffeine free so sleep disruption is not anticipated. There is also a risk of hepatotoxicity associated with the consumption of EGCG.

**3. In terms of emotional distress,** some subjects might be distressed at their performance in some of the GA measures. Some measures e.g. the geriatric depression scale contains sensitive questions. Subjects are not required to answer any questions for any reason.

**4. In terms of loss of confidentiality,** both quantitative data and biological samples from subjects will need to be stored. Thorough, rigorous, and well-tested data safety and security guidelines will be observed, there is still a chance that confidentiality could be breached and sensitive medical information could become known to persons outside the research team. There is also a small chance that a subject's identity could be revealed if our secure data servers are broken into.

## **8.2 Adequacy of protection against risk**

We will protect against all study risks, which are:

1. Physical harm associated with assessment and intervention procedures
2. Emotional distress
3. Loss of confidentiality

### **1. Physical harm associated with assessment and intervention procedures:**

Every effort will be made to minimize the risks associated with study procedures for all subjects. First, all subjects must have the approval of their physician to enter the study. Research personnel will assess patient's ability to conduct any of the physical assessments before patient's attempt. Physical tests will only be performed if it is safe to do so. When a subject is completing any of the physical tests, the research personnel will stay behind and to the side of the subject to assist in the case the subject loses balance or begins to fall. When using chairs, the chairs will be positioned so they do not move (e.g. chair's back will be placed against the wall).

### **2. Emotional distress:**

To prevent distress, subjects will be informed that they are free to decline to answer any question for any reason. Research staff will be extensively trained to help minimize distress to subjects. However, should subjects become depressed, anxious, agitated, or otherwise distressed during the assessment, a trained member of the research staff will be notified

and the subject will be triaged and referred for care. Should the subject already be receiving care, they will be referred to follow up with their care provider and a check in call will be made following the assessment to establish subject safety and comfort.

#### **4. Confidentiality:**

This study involves collecting biological samples, data from clinical and self-reported assessments, obtaining access to medical records, and communicating via email. Thus, steps must be taken to protect both subject data and identity. The following confidentiality protection steps will be taken:

1. Research staff will participate in initial training, follow-up training, and ongoing monitoring and supervision to ensure understanding of the ethical issues involved in this research. Training will be provided in accordance with URMC policies (e.g., online coursework via the CITI collaborative, ongoing discussions with senior scientific colleagues).
2. Only the research staff will know the name, identification (ID) number, and contact information of subjects. The list that links the subject's name with ID number will be kept on an encrypted drive accessible only by the research staff.
3. Consent forms will be kept in locked filing cabinets in a locked office, again accessible only by research staff.
4. Any personal identifiers linked to data will be removed and replaced by non-identifying ID numbers in all records. The electronic files that contain quantitative data will be stored on a secure University of Rochester Medical Center file server. These files will be password-protected and accessible only by the study staff.
5. The risk of email communication is included in our Consent Form.
6. While first names will be used in individual interviews in order to facilitate discussion and comfort with the research interviewer, all personal identifiers will be deleted (e.g. de-identified) from the transcriptions of the audio-recordings. All study data will be stored in locked cabinets and electronic files will be stored using HIPAA-compliant storage solutions. Audio recorded data will be kept for approximately 5 years.

### **8.3 Benefits**

There may or may not be any direct benefits of the study to the study subjects. The potential benefit to the subject from being in this study might be receiving the results from some of the tests, possibly enabling better insight and awareness into the subjects' health.

### **8.4 Alternatives to participation**

The subject may choose to not participate in the study without penalty or effects on subsequent medical care, etc.

---

## **9. CONFIDENTIALITY OF DATA AND DATA STORAGE**

---

### **9.1 Utilizing Research Electronic Data Capture (REDCap)**

Study data will be collected via paper forms then study personnel will electronically enter participant data into a web-based survey administered using REDCap software. REDCap is a secure, web-based application for building and managing online surveys and databases and is made available through the University of Rochester Clinical and Translational Science Institute. REDCap will be used to send a secured web link to each study subject, and a built-in scheduling function will allow for re-contact at a pre-specified time to remind subjects to assessments if needed. All data forms will be checked immediately by the REDCap system as they are being completed by the study personnel to ensure completeness (i.e., that no question was skipped unintentionally), and a pop-up message feature will be used to encourage a response. Once data collection is complete, REDCap provides an automated export procedure for data download. Every effort will be made to reduce attrition and obtain follow-up data. Steps will be taken to avoid missing data. If subjects do not complete surveys after receiving a follow-up reminder, the study coordinator will attempt to contact the subject via phone and ask if they are willing to give their responses verbally for the study staff member to enter into the REDCap database.

### **9.2 Data storage**

All hardcopy research records will be stored onsite in the University of Rochester Medical Center and in the Cancer Control. The Cancer Control Unit is located in the Saunders Research Building,

in an office suite secured by electronic key cards. Electronic research records are stored on the University of Rochester Medical Center's password secured and firewall protected networks. These are the same methods of security used for subject medical records. Human serum samples are stored in locked freezers, within secured areas of the Medical Center that are accessible by key codes and electronic card swipes.

All study data will be kept for a period of at least six years after the study and all reports and publications are complete.

### **9.3 Human blood samples**

All data (information and human blood samples) collected for the current study will be used in post hoc analyses as appropriate. Blood samples will be banked and data will be used for future studies only with prior consent of subjects. The consent form contains appropriate language related to banking and subjects are given the option to have their samples banked or to have them destroyed following analysis of the study hypotheses. Subjects' individual research records will not be shared with their treating physician, unless they provide consent or the subject's treating physician is a study physician, in which case they will have access to study data as a study co-investigator. Overall study results may be presented to subjects, faculty and staff at the University of Rochester Medical Center after completion of the study. Study results will be presented at professional meetings, published, and reported on clinicaltrials.gov.

### **9.4 Assignment of study ID**

The study team will assign a numerical Study ID to each subject once they have signed the consent form. Study forms and questionnaires will use this number and the subject's first and last initials as identifiers to ensure data integrity. Other identifying information will not exist on these forms. A complete list of study subjects with study ID, name, and contact information will be maintained separately for the purpose of contacting subjects for phone call or e-mail reminders; this database will be maintained until at least six years after the study is complete. This linkage information will only be accessible to the study chair, study investigators, and the individual responsible for maintaining the database.

---

## 10. RESEARCH INFORMATION IN MEDICAL RECORDS

---

Documentation of study participation will be included in the medical record by means of uploading a signed consent form to each subject's medical record. Subjects' blood draw will also be noted in the medical record. For the duration that patients are on-study (13 weeks) their electronic records will indicate their active participation. After study participation is complete, this indication will be removed. No further research-related information will be included in the medical record.

---

## 11. DATA ANALYSIS AND DATA MONITORING

---

[figure not shown]
### 11.1 Sample size determination

We plan to enroll 40 subjects (20;  $\geq 6$  AA/B per arm). Evaluation of recruitment and adherence to the intervention is required for planned future Phase 2/3 frailty trials in older cancer survivors.

*Aim 1:* With a feasibility target of 70% of

Protocol Date: January 2016

44

randomized subjects completing the study we expect at least 14 evaluable patients per arm, which is appropriate for small randomized studies and it will allow us to obtain preliminary estimates of descriptive statistics (mean, standard deviation (SD), and confidence intervals (CI)). *Aim 2:* At significance level  $\alpha=0.15$ ,  $N=14$  per arm will provide 70% power to detect effect size (standardized mean change in frailty score) of 0.66, if pre-post correlation=0.5 (conservative estimate for FFS; Figure 5).

**Analyses:** *Aim 1:* For each feasibility outcome (recruitment and adherence), we will evaluate proportions of subjects meeting criterion and report percentages with CIs. For AEs, we will report the total and severity of AE's per group. *Aim 2:* Descriptive statistics will be calculated at baseline, post-intervention, and for pre-post change scores for subjects in EGCG and UC arms. To evaluate the preliminary efficacy estimates of EGCG on FFS we will use an analysis of covariance (ANCOVA) model (outcome=FFS at post, covariates: FFS at baseline and arm). Estimates of distribution characteristics (e.g., mean, variance, pre-post correlation) and preliminary estimates of efficacy will inform the design and sample size of our planned future study. *Aim 3:* Similar analyses to Aim 2 will be performed for TNF- $\alpha$ , TNFRI, TNFRII, IL-6, IL-1 $\beta$ , and CRP. If data for inflammatory markers are missing due to lower limit of detection, we will use appropriate imputation methods. *Aim 4:* Using similar analyses to Aim 2, we will conduct preliminary subgroup analyses by race and treatment type.

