### **2.1 Overall hypothesis**

We hypothesize that EGCG supplementation will reduce markers of inflammation and frailty, is safe and feasible, and will improve physical function, patient reported symptoms, and quality of life in older patients with cancer post-surgery with or without chemotherapy.

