### **2.3 Study Outcomes**

***Aim 1:*** To determine the feasibility and safety of conducting a two arm RCT as measured by recruitment rate, adherence to study procedures and EGCG intervention, and adverse events.

***Aim 2:*** To obtain preliminary data on the effects of EGCG vs UC on frailty measured by FFS (weight loss, weakness measured by hand-grip dynamometry, slowness measured by 4 meter walk test, physical activity measured by the GODIN Leisure-Time Physical Activity, and exhaustion

measured by the symptom inventory) and the Deficit Accumulation Frailty Index (DAFI) based on the geriatric assessment.

**Aim 3:** To obtain preliminary data on the effects of EGCG vs UC on TNF- $\alpha$  related immune responses (measured by serum levels of TNF- $\alpha$ , TNFR I, TNFRII, IL-6, IL-1 $\beta$ , and CRP) and circulating immune cells as measured by lymphocytes, monocytes, neutrophils, total WBC, NLR, LMR in older survivors of CC.

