## **5.6 Randomization**

Randomization will be revealed to the subject at the end of the baseline assessment and immediately before delivering the study drug.

We will employ two arms in a 1:1 allocation ratio:

1. EGCG: 12 weeks daily of 800mg EGCG +250mg VitC taken 1 time a day at breakfast (four 200mg EGCG capsules will be packaged with one 250mg VitC tablet)
2. Usual care

Consented subjects will be randomized with a computer-generated random numbers table with block sizes of 2. We will stratify by race (Black vs other) and treatment type (surgery vs other).

The random numbers tables will be generated centrally using software provided by [name], the project biostatistician. A total enrollment of 40 subjects is planned. Due to the study design the PI, study subjects, personnel, and statisticians will be un-blinded to the treatment assignments.

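### Safety is part of Aim 1, but adverse events are to be reported only as totals and severity per arm, with no count of subjects affected, no denominator and no interval

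*Combined protocol and SAP*

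**What the plan says.** Section 2.3 states Aim 1 as "To determine the feasibility and safety of conducting a two arm RCT", and lists adverse events among its measures. Section 2.1 hypothesizes that "EGCG supplementation will reduce markers of inflammation and frailty, is safe and feasible", and the theoretical framework in section 1.4 also puts safety among the things to be determined.

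The Analyses paragraph of section 11.1 treats the Aim 1 outcomes in two ways:

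- Feasibility: "For each feasibility outcome (recruitment and adherence), we will evaluate proportions of subjects meeting criterion and report percentages with CIs".
- Adverse events: "For AEs, we will report the total and severity of AE's per group".

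The sample size text in the same section mentions confidence intervals for Aim 1 as general descriptive statistics, but does not tie them to adverse events.

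Sections 5.9, 7 and 11.3 add weekly enquiry, CTCAE grading, attribution, stopping criteria and committee review. These govern monitoring and reporting during the trial. None of them plans a final count of subjects with at least one event, a worst grade per subject, a safety denominator or an interval.

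**The concern.** Two separate things are missing.

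**The unit of analysis.** "For AEs, we will report the total and severity of AE's per group" does not define what is totalled. The natural reading is events. An event total mixes how many subjects are affected with how many events each of them has, and a severity breakdown of events does not separate the two. In an arm of 20, one subject with several new, recurring or worsening events can account for much of the total.

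**The precision.** With no denominator and no interval, a low or zero count stands without any indication of what rates remain compatible with it. This bears most on hepatotoxicity, which section 8.1 names as a risk. Section 7 stops the study if a drug-related hepatotoxicity of Grade 3 or higher is seen in the intervention arm. A trial that runs to its planned end will therefore almost always show zero such events, and the upper limit is then the informative result.

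At stake is how the safety part of Aim 1 is expressed, and what the planned later trials can take from it.

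**Working it through.** **Inputs**

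- Enrolment: "We plan to enroll 40 subjects (20" per arm, section 11.1. Section 5.6 agrees: "We will employ two arms in a 1:1 allocation ratio", so 40 / 2 = 20 assigned to EGCG.
- Exposed subjects: taken as 20, assuming everyone assigned to EGCG takes at least one dose. If fewer do, the limits below rise.
- Confidence level for safety: not given in the documents. Two-sided 95% is assumed, with alternatives shown. Section 11.2 tests hypotheses at two-sided alpha 0.15, which corresponds to an 85% interval.

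**The plan's own figure.** No precision figure is stated for safety, so there is none to reproduce. The evaluable number in section 11.1 does reproduce: 20 × 0.70 = 14 per arm. That is a count of completers and is not used as the safety denominator here.

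**Step 1: what a total of five events can mean.** The exact (Clopper-Pearson) limits for x of n are the 0.025 quantile of Beta(x, n − x + 1) and the 0.975 quantile of Beta(x + 1, n − x). With n = 20:

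| Subjects behind 5 events | Proportion | Exact 95% CI |
|---|---|---|
| 1 (all five events) | 5% | 0.1% to 24.9% |
| 5 (one event each) | 25% | 8.7% to 49.1% |

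The planned total is 5 in both rows.

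**Step 2: what zero of 20 leaves open.** For a zero count the exact upper limit is 1 − a^(1/n), where a is the upper-tail error.

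| Level | a | Upper limit, n = 20 |
|---|---|---|
| Two-sided 95% | 0.025 | 1 − 0.025^(1/20) = 16.8% |
| One-sided 95% | 0.05 | 1 − 0.05^(1/20) = 13.9% |
| Two-sided 85% | 0.075 | 1 − 0.075^(1/20) = 12.1% |

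The two-sided 95% Wilson limit is 16.1%, and the rule of three gives 3/20 = 15%. Choice of method matters little.

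**Step 3: how often zero would be seen anyway.** The chance of no affected subject among 20 is (1 − p)^20. At a true rate of 5% it is 0.95^20 = 35.8%; at 10% it is 0.90^20 = 12.2%.

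**The case against.** The strongest reply is that this is a 40-subject feasibility trial with descriptive safety reporting, no safety test and no threshold. Several parts of that reply stand.

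- A reader might infer that zero severe events would be read as proof of safety, or that the safety hypothesis would be declared met. The documents contain no such rule. Sections 1.4 and 2.1 state a hypothesis, not a decision criterion.
- A reader might infer that a complaint repeated unchanged at each weekly contact inflates the total. Sections 5.9 and 7 limit adverse events to things that develop or worsen, so an unchanged complaint should not be counted again. The argument covers only distinct, recurring or worsening events.
- A reader might compute limits on the completers, since section 11.1 says "With a feasibility target of 70% of" "randomized subjects completing the study we expect at least 14 evaluable patients per arm". Completers are not the safety denominator: adverse events are sought weekly from every subject, and section 11.2 analyses subjects as randomized.
- The 16.8% limit comes from 20 subjects and a chosen 95% level, not from counting events. With no events, event and subject counts agree, and anyone who knows the arm size can work out the limit. Printing an interval does not let the trial exclude a smaller rate.
- Severity is planned, and liver events have scheduled tests and subject-level stopping criteria.

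What remains is that monitoring rules do not supply the final analysis. Nor does small size excuse the omission: the plan already commits to intervals for the other Aim 1 outcomes, and an interval is most useful when the arm is small.

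**Conclusion.** The concern holds as a gap in the planned safety summary. Section 11.1 names a specific method for adverse events that gives no number or proportion of subjects affected, no denominator and no interval, and no other section supplies them.

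Its size is twofold. The same total of 5 events is compatible with 1 of 20 or 5 of 20 subjects affected. A zero among about 20 exposed leaves rates up to 16.8% open at two-sided 95%, or 12.1% to 13.9% at the less strict levels shown. The conclusion is the same across that range.

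It rests on reading the total as a count of events, on about 20 exposed subjects, and on a confidence level that the documents do not set. It does not show that the trial would draw a wrong safety conclusion. It is a cheap improvement to reporting, not a defect in the design or conduct.

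**What to change.** Replace the adverse event sentence in section 11.1 with:

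> For each arm, report the number and proportion of subjects with at least one AE, by worst CTCAE grade and attribution, with exact 95% CIs. The denominator is all randomized subjects in usual care and all who took at least one dose in the EGCG arm. Event totals are supplementary. Where no subject has the event, including Grade 2 or higher and Grade 3 or higher liver events in the EGCG arm, report the upper limit.

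Word the safety conclusion as the rate that can be excluded. The liver statement is confined to the EGCG arm because section 5.9 schedules the week 4 and week 8 liver tests only there, so liver event counts are not ascertained alike in the two arms.

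The cost is one sentence, one extra table and a more modest safety statement. Grading and attribution are already planned, so no new data, subjects or clinical rules are needed.

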#### Other Measures for DAFI calculation

*Physician rated Karnofsky Performance Status (KPS):* The KPS is an index that allows patients with cancer to be classified according to the presence of any functional impairments (e.g. inability to work and care for personal needs). KPS score ranges from 0-100. Low KPS scores are associated with decreased survival in patients with cancer.

*Patient rated KPS:* The patient rated KPS is a patient reported outcome of the presence of any functional impairments.

*Complete Metabolic Panel (CMP):* Study personnel will obtain lab results from the CMP from electronic medical records with dates that are closest to assessment date for baseline assessment (T1) and post-intervention assessment (T2).

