## **5.7 Study Interventions (12 weeks' duration)**

**Arm 1:** EGCG: 800mg EGCG +250mg VitC taken 1 time a day. Subjects will a bag with 84 light resistant pill pouches. Each pill pouch will contain four 200mg EGCG capsules with one 250mg VitC tablet. Subjects will be instructed to take all the contents of each pill pouch every day at breakfast for a period of 12 weeks. Subjects will be monitored monthly for hepatotoxicity (liver function test of ALT, AST, and bilirubin). Subjects will receive a weekly phone call to assess any safety concerns and to assess adherence.

**Arm 2:** Usual care – Subjects will be assigned to usual care during the course of the study. Subjects will receive a weekly phone call as a check in.

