## **5.9 Intervention contact and tracking**

The study coordinator will make every effort to contact each subject 1 time per week via phone calls, and/or emails, (based on each subject's preference) to encourage intervention adherence to the study drug. During this weekly contact the study coordinator will also ask about any safety concerns including: symptoms, signs, illnesses, or experiences, that develop or worsen during the study. These concerns will be graded (according to the CTCAE v5.0 see section 7), recorded, reviewed with the treating oncologist as well as the medical monitor, and reported (if necessary) according to the outline in section 7. If medical information needs to be further discussed, we will set up a phone call, virtual meeting or face-to-face meeting. Study contact will occur from our research staff, which includes study PI, the study staff (coordinators, etc.), and the patient's treatment team (e.g., oncologists, nurses, staff, etc.).

Subjects in the intervention arm will report to URMC labs at weeks four and eight after baseline for a lab draw to determine liver function (ALT, AST, and bilirubin) so that any hepatotoxicity can be monitored. Study personnel will call subjects to remind and coordinate the blood draws.

To track adherence, we will instruct subjects to bring all remaining study drug at their post-intervention assessment (T2) and the pills will be manually counted and pill counts will be entered onto the pill excel document.

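### Per-group AE totals will mix findings from liver tests scheduled only in the EGCG arm with findings sought in both arms

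*Combined protocol and SAP*

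**What the plan says.** Safety is part of Aim 1 (section 2.3), and adverse events are one of its named measures. The whole AE analysis is one sentence in section 11.1: "For AEs, we will report the total and severity of AE's per group". Sections 11.2 and 11.3 add no display by how an event was detected.

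On liver tests, section 5.7 says under Arm 1 only: "Subjects will be monitored monthly for hepatotoxicity (liver function test of ALT, AST, and bilirubin". Section 5.9 gives the timing: "Subjects in the intervention arm will report to URMC labs at weeks four and eight after baseline for a lab draw". Section 5.11 agrees, since it pays for hepatotoxicity draws in the intervention arm only. In both arms, section 5.5 takes metabolic panel values from charts at the dates nearest T1 and T2: "Study personnel will obtain lab results from the CMP from electronic medical records". Table 4 lists a liver function test among the items used.

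On weekly contact, section 5.7 describes the Arm 1 call as follows: "Subjects will receive a weekly phone call to assess any safety concerns and to assess adherence". For Arm 2 it says: "Subjects will receive a weekly phone call as a check in". Section 5.9 makes no such distinction: "The study coordinator will make every effort to contact each subject 1 time per week via phone calls". It then has the coordinator ask about safety concerns at that contact and has them graded and recorded.

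Section 7 defines an AE as any symptom, sign, illness or experience that develops or worsens on study, related or not. Its Grade 1 includes symptomless findings seen only on a diagnostic test.

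**The concern.** A per-group total is informative about the supplement only if events are looked for in the same way in both groups. Most mild liver enzyme changes cause no symptoms, so they are found only when blood is tested. The plan tests for them mid-study in one arm and not in the other, then puts the results in the same total. Extra Grade 1 findings also change the severity mix.

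At stake is the safety part of Aim 1 and the use of these data to plan a later trial. Hepatotoxicity is a named risk in section 8.1, so an excess of liver findings under EGCG is what a reader would expect to see, and would readily attribute to the supplement. With 20 subjects per arm, a few findings can change the impression the table gives.

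**Working it through.** **1. No plan figure to reproduce.** The documents give no AE rate, no AE sample size and no method for comparing AEs between arms. The Aim 2 power statement does not bear on this point.

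**2. Which liver results can enter each arm's total**

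| Source | EGCG | Usual care |
|---|---|---|
| Chart values nearest T1 and T2 (5.5, Table 4) | yes | yes |
| Scheduled tests at weeks 4 and 8 (5.7, 5.9, 5.11) | yes | no |
| Found clinically or reported at weekly contact | yes | yes, if 5.9 is followed |

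Only the second row differs by design.

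**3. Whether those results count as AEs.** Under section 7 a laboratory abnormality that is new or worse is a sign, relatedness is not required, and Grade 1 admits symptomless diagnostic findings. Exclusion criterion 2 applies only at 3 or more times the upper limit of normal. Subjects with milder elevations can therefore enrol; a stable elevation would not be an AE, but a worsening one would.

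**4. Upper illustration of size**

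Inputs: 20 subjects per arm (11.1); 2 extra draws per EGCG subject (5.9). Assumptions: no true EGCG effect, full attendance, every abnormal panel counted as a new AE, and the same chance q of an abnormal panel at each draw. The q values are assumed, because the documents give none.

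- Extra draws: 20 x 2 = 40 under EGCG, 0 under usual care.
- Expected extra findings: 40 x q.
- Chance of at least one, if draws are independent: 1 - (1 - q)^40.

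| Assumed q | Expected extra findings | Chance of at least one |
|---|---|---|
| 2% | 40 x 0.02 = 0.8 | 55.4% |
| 5% | 40 x 0.05 = 2.0 | 87.1% |
| 10% | 40 x 0.10 = 4.0 | 98.5% |

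**5. Relaxing the assumptions**

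- Attendance: if only 14 of 20 EGCG subjects had both draws (using the 70% completion target in 11.1 as a stand-in), there are 14 x 2 = 28 draws, giving 28 x q = 0.56, 1.4 and 2.8.
- Repeat findings: if an abnormality at week 4 always persists to week 8 and is counted once, the expectation is 20 x q = 0.4, 1.0 and 2.0.
- New or worse only: removing stable baseline elevations lowers every figure. The documents give nothing from which to size this.

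**6. The weekly call.** Section 5.7 read alone suggests that only Arm 1 is asked about safety. Section 5.9 says each subject is contacted and asked, and the section 5.3 table, which covers all subjects regardless of arm, includes the Weekly Phone Call Log. On the other side, 5.9 gives encouragement of study-drug adherence as the purpose of the contact, which can apply only to EGCG, and the log entry does not show what is asked. If 5.9 is followed in both arms, the call causes no designed excess of symptom AEs. If 5.7 is read literally it could, but the documents give no rate from which to size it.

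**The case against.** The best defence is that the AE summary is purely descriptive. Section 11.1 plans no test, interval or threshold for a between-arm AE difference, and the hepatotoxicity stopping criteria in section 7 concern intervention subjects only. That is correct, and it limits the consequence. It does not remove the problem, because totals set side by side by group invite comparison and the distortion arises in how events are found, with or without a test.

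Two stronger readings are tempting. A reader might infer from 5.7 that usual care subjects are not asked about safety, so that all AEs are under-detected there. The documents do not establish this, given 5.9 and the call log in 5.3; what remains is a conflict of wording. A reader might also infer that the EGCG total will come out higher even with an inert supplement. That does not follow either. Without AE rates, the extra findings cannot be weighed against all other AEs, chance could hide or reverse the excess, and at q = 2% there is about a 45% chance of no extra finding at all (100% - 55.4%).

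A further objection concerns the remedy. Simply removing the week 4 and 8 findings from the EGCG total could understate a known harm, since an event caught early would vanish from the main count. This stands, and is why the totals should be shown both ways, with the full liver results alongside.

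**Conclusion.** The concern holds for laboratory liver findings. The week 4 and 8 tests are in the EGCG arm only, their symptomless results qualify as AEs under section 7, and the summary in 11.1 makes no allowance for this. The expected effect is to raise the EGCG count relative to usual care when there is no drug effect.

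The size is modest but relevant at 20 per arm: at most about 0.8 to 4 expected extra findings for assumed per-draw rates of 2% to 10%, and fewer with missed draws, persistent abnormalities counted once, or stable baseline elevations left out. These figures rest on assumed rates and show scale only. Bias across all AEs is not shown. The difference between 5.7 and 5.9 on the weekly call is an inconsistency to resolve, not evidence of unequal questioning.

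**What to change.** In section 11.1, Aim 1 analyses:

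- Label each AE by how it was detected: weekly contact, clinical presentation, a time point common to both arms, or the week 4 or 8 liver test.
- Report totals and severity per group twice, including and excluding findings detected only by the week 4 and 8 tests. Base the between-group description on the version with common ascertainment.
- Keep in the main totals any liver event also found clinically or at a time point common to both arms.
- Show all week 4 and 8 liver findings in full in a separate EGCG-arm table.

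Separately, reconcile 5.7 with 5.9 by stating that the same AE questions are asked at the weekly contact in both arms. With staff and subjects unblinded (5.6), a shared script is worth having.

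Cost: one extra table, a slightly longer AE summary, a detection-route field on the AE record and an agreed call script. No draws are added, and the monitoring and stopping rules are unchanged.
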